#### **5.2.6.2 Adverse event collection and reporting**

##### **5.2.6.2.1 AE Collection**

The investigator shall maintain and keep detailed records of all AEs in the patient files. The following must be collected and documented on the appropriate CRF(s) by the investigator:

- From signing the informed consent onwards until the individual patient's end of trial: all AEs (serious and non-serious) and all AESIs.
- After the individual patient's end of trial:  
the investigator does not need to actively monitor the patient for new AEs but should only report cancers of new histology and exacerbations of existing cancer and trial treatment related SAEs and trial treatment related AESIs of which the investigator may become aware of by any means of communication, e.g. phone call. Those AEs should be reported on the BI SAE form (see section 5.2.6.2.2), but not on the CRF.

##### **5.2.6.2.2 AE reporting to the sponsor and timelines**

The investigator must report SAEs, AESIs, and non-serious AEs which are relevant for the reported SAE or AESI, on the BI SAE form via fax immediately (within 24 hours) to the sponsor's unique entry point (country specific contact details will be provided in the ISF). The same timeline applies if follow-up information becomes available. In specific occasions,

the investigator could inform the sponsor upfront via telephone. This does not replace the requirement to complete and fax the BI SAE form.

With receipt of any further information to these events, a follow-up SAE form has to be provided. For follow-up information the same rules and timeline apply as for initial information. All (S)AEs, including those persisting after individual patient's end of trial must be followed up until they have resolved, have been assessed as "chronic" or "stable", or no further information can be obtained.

#### **5.2.6.2.3 Pregnancy**

In rare cases, pregnancy might occur in a clinical trial. Once a patient has been enrolled in the clinical trial and has taken trial medication, the investigator must report any drug exposure during pregnancy in a trial participant immediately (within 24 hours) by means of Part A of the Pregnancy Monitoring Form to the sponsor's unique entry point.

The outcome of the pregnancy associated with the drug exposure during pregnancy must be followed up and reported to the sponsor's unique entry point on the Pregnancy Monitoring Form for Clinical Trials (Part B).

The ISF will contain the Pregnancy Monitoring Form for Clinical Trials (Part A and B).

As pregnancy itself is not to be reported as an AE, in the absence of an accompanying SAE and/or AESI, only the Pregnancy Monitoring Form for Clinical Trials and not the SAE form is to be completed. If there is an SAE and/or AESI associated with the pregnancy an SAE form must be completed in addition.

#### **5.2.7 Criteria for hypoglycemic events**

Every episode of plasma glucose  $\leq 70$  mg/dl ( $\leq 3.9$  mmol/l) should be documented in the eCRF with the respective time and date of occurrence. Such hypoglycemic events should be documented in the eCRF according to the following criteria:

- Asymptomatic hypoglycemia: event not accompanied by typical symptoms of hypoglycemia but with a measured plasma glucose concentration  $\leq 70$  mg/dl (3.9 mmol/l)
- Documented symptomatic hypoglycemia with glucose concentration  $\geq 54$  mg/dl and  $\leq 70$  mg/dl ( $\geq 3.0$  mmol/l and  $\leq 3.9$  mmol/l): event accompanied by typical symptoms of hypoglycemia
- Documented symptomatic hypoglycemia with glucose concentration  $< 54$  mg/dl ( $< 3.0$  mmol/l): event accompanied by typical symptoms of hypoglycemia
- Severe hypoglycemic episode: Event requiring the assistance of another person to actively administer carbohydrate, glucagon or other resuscitative actions.

Note for severe hypoglycemia: If another person hands the carbohydrate or glucagon to the patient without having to actively administer the substance because the patient is able to take the substance on his or her own, the hypoglycemic episode does not qualify as severe.

Any hypoglycemia with glucose values  $< 54$  mg/dl ( $< 3.0$  mmol/l) and all symptomatic or severe hypoglycemia events should be documented as an adverse event of hypoglycemia.

Further details on documentation of hypoglycemia are provided on the respective eCRF pages.

### 5.3 DRUG CONCENTRATION MEASUREMENTS AND PHARMACOKINETICS

Not applicable.

### 5.4 ASSESSMENT OF BIOMARKER(S)

This section refers to exploratory biomarkers. Established biomarkers of efficacy and safety are described and discussed in [sections 5.1](#) and [5.2](#).

#### 5.4.1 Biochemical and cellular biomarkers

Biomarker assays will be measured in a central laboratory.

- 1) C-peptide
- 2) Insulin

C-peptide will be tested with the sample collected on Visit 3 and Visit 8 at both fasting and postprandial status to assess the beta cell function, which will contribute to a better understanding of the influence of Empagliflozin in combination with insulin on the course of disease in the patients with T2DM.

Based on the analysis of fasting plasma insulin (FPI) and FPG, the Homeostasis Model Assessment (HOMA) indices will be derived in the following way [[R07-1029](#)]:

HOMA-Index (to assess insulin resistance (IR))

$$\text{HOMA-IR} = [\text{FPG (mmol/L)} \times \text{FPI (mU/mL)}] / 22.5$$

HOMA-Index (to assess insulin secretion)

[figure not shown]
$$\text{HOMA-}\beta = (20 \times \text{FPI (mU/mL)}) / (\text{FPG (mmol/L)} - 3.5)$$

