### **3.3.2 Inclusion criteria**

1. Age  $\geq 18$  years and  $\leq 75$  years old at Visit 1;
2. Chinese patient with diagnosis of Type 2 diabetes prior to Visit 1;
3. A stable treatment with premixed Insulin ( $\geq 20$  IU/day) or basal insulin ( $\geq 16$  IU/day) for at least 12 weeks prior to enrolment with or without up to two OADs
  - With maximum insulin dose of  $\leq 1$  unit/kg/day. Acceptable basal insulins should have duration of action up to 24 h such as insulin Degludec, insulin glargin, insulin detemir or NPH (neutral protamine hagedorn) insulin; Acceptable pre-mixed insulins could be once or twice daily posology only. The total insulin dose should not be changed by more than 20% of the baseline value within the 12 weeks prior to randomisation (Visit 3). Both human insulin & insulin analogue are acceptable;
  - If the patient is taking OADs, regimen has to be unchanged for at least 12 weeks prior to randomization (Visit 3);
  - If the patient is taking metformin, stable dose (at least 1500 mg daily or maximum tolerated dose) must be maintained for at least 12 weeks without dose adjustments prior to randomization (Visit 3);
4. HbA1c  $\geq 7.5\%$  and  $\leq 11.0\%$  at Visit 1;
5. Fasting C-peptide:  $>0.5$  ng/mL ( $>166$  pmol/L) at Visit 1;
6.  $18.5 \text{ kg/m}^2 \leq \text{BMI} \leq 45 \text{ kg/m}^2$  at Visit 1;
7. Signed and dated written informed consent in accordance with ICH-GCP and local legislation prior to admission to the trial;
8. Male or female patients. Women of childbearing potential (WOCBP) must be ready and able to use highly effective methods of birth control per ICH M3 (R2) that result in a low failure rate of less than 1% per year when used consistently and correctly. A list of contraception methods meeting these criteria is provided in the patient information.

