## 4.2 OTHER TREATMENTS, EMERGENCY PROCEDURES, RESTRICTIONS

### 4.2.1 Other treatments and emergency procedures

Throughout the duration of the trial, patients should continue to take insulin alone or in combination with acceptable OADs as background therapy.

Acceptable basal insulins should have duration of action up to 24 h such as insulin degludec, insulin glargin, insulin detemir or NPH (neutral protamine hagedorn) insulin. The background medication of OADs should remain unchanged throughout the study. Acceptable pre-mixed insulins could be once or twice daily posology only. The total prescribed insulin dose should not be changed by more than 10% of the baseline value in the 24 weeks after randomisation unless rescue therapy criteria for treatment of hyperglycemia are met or in case of hypoglycemia requiring insulin dose reduction beyond the defined limits. The background medication will not be provided as part of the clinical trial supplies.

The patients can take their background medication as they are used to and should have the same habits of dosing throughout the trial, where it is suggested that basal insulin is always given in the evening. Morning dose of OADs/any permitted pre-mixed insulin and study medication should be taken after the visits blood sample taken.

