## **5.7 APPROPRIATENESS OF MEASUREMENTS**

All measurements performed during this trial are standard measurements and will be performed in order to monitor safety aspects in an appropriate way.

The scheduled measurements are appropriate to see drug induced changes in vital signs, standard laboratory values, biomarkers specific to efficacy of treatment of T2DM, and ECG. The primary and secondary endpoints are standard and accepted for evaluation of safety and tolerability of an oral antidiabetic drug, and they are widely used in respective pivotal phase III studies.

Measurements of insulin and c-peptide will be conducted in order to characterise endogenous insulin production and will contribute to a better understanding of the influence of empagliflozin combination with insulin with or without OADs on the pathogenesis and possible recovery of diabetes in the patients.

Therefore, the appropriateness of all measurements applied in this trial is given.

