7 PLANNED ANALYSES

Disposition of the patient population participating in the trial will be analysed by treatment groups and presented in the clinical trial report as a frequency-distribution. The number of patients participating in the study will also be analysed by treatment group and presented as a frequency distribution.

A frequency of patients with iPDs, also summarised by whether the iPD led to exclusion from the PPS, will be presented by treatment group for treated set. The frequency of patients in different analysis sets will also be presented for each treatment group.

For in-text tables presenting descriptive analysis of the endpoints and other variables (analysed in original scale), the set of summary statistics is: N (number of patients with non-missing values), mean, standard deviation (SD).

For end-of-text tables, the set of summary statistics is: N (number of patients with non-missing values) / Mean / SD / Min / Q1 (lower quartile) / Median / Q3 (upper quartile) / Max.

For the in-text, end-of-text and appendix tables presenting descriptive analysis of the endpoints and other variables (analysed on logarithmic scale), the respective summary statistics (e.g., gMean, gCV, etc.) will be used.

Statistical parameters will be displayed to a defined number of decimal places as specified in the BI guideline "Reporting of Clinical Trials and Project Summaries" (2). Patient level results for the calculated endpoints HOMA-IR will be presented to one decimal place.

HOMA- β will be presented as full integers. The summary statistics of these parameters will follow the aforementioned guideline.

Tabulations of frequencies for categorical data will include all possible categories and will display the number of observations in a category as well as the percentage (%) relative to the respective treatment group. Percentages will be rounded to one decimal place. The category missing will be displayed if and only if there are actual missing values. Percentages will be based on all patients in the respective patient set whether they have non-missing values or not.

In all specified statistical analyses, treatment comparisons will be made between each randomised empagliflozin group (10mg and 25mg) and placebo.

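### HOMA-β and HOMA-IR are derived from fasting plasma insulin although every patient injects insulin, so HOMA-β cannot be read as endogenous secretion

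*Protocol*

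**What the plan says.** Protocol Section 5.4.1 defines both indices from the same two inputs: "Based on the analysis of fasting plasma insulin (FPI) and FPG, the Homeostasis Model Assessment (HOMA) indices will be derived in the following way". HOMA-IR is FPG × FPI / 22.5 and is labelled as assessing insulin resistance. HOMA-β is 20 × FPI / (FPG − 3.5) and is labelled as assessing insulin secretion. The same section assigns fasting and postprandial C-peptide at Visits 3 and 8 to beta-cell function. Section 5.7 gives the purpose: "Measurements of insulin and c-peptide will be conducted in order to characterise endogenous insulin production".

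All patients are on injected insulin. Inclusion criterion 3 (Protocol Section 3.3.2) requires stable premixed or basal insulin "for at least 12 weeks prior to enrolment with or without up to two OADs", so the oral drugs are optional and the insulin is not. Under Section 4.2.1, "patients should continue to take insulin alone or in combination with acceptable OADs as background therapy". That section accepts basal insulins acting for up to 24 hours, and "it is suggested that basal insulin is always given in the evening". On visit days only the morning doses wait until blood has been drawn.

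The SAP carries the indices forward. Section 6.6.6 calculates HOMA-β only when FPG exceeds 3.5 mmol/L. Table 6.7:1 lists biomarkers of insulin resistance and secretion among the efficacy endpoints. Section 7 sets display precision ("Patient level results for the calculated endpoints HOMA-IR will be presented to one decimal place", with HOMA-β as integers), and Section 7.1 includes both indices in the baseline description. No visible text in either document deals with injected insulin in the fasting sample, names the insulin assay, or says whether it detects insulin analogues.

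**The concern.** Both formulas treat fasting insulin as the patient's own. An evening basal dose with up to 24 hours of action is still working when the fasting sample is taken the next morning. Holding the morning dose does not remove it. HOMA-β then counts detected injected insulin as beta-cell output, and HOMA-IR is raised by the same factor.

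At stake is the interpretation of an exploratory result. A table headed insulin secretion would report a quantity that differs from the endogenous production named in Section 5.7. It could also show an apparent improvement in the active arms that comes from the formula and not from the beta cell.

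**Working it through.** The plan states no figure for these indices, so there is nothing to reproduce. The formulas are those of Protocol Section 5.4.1. All insulin and glucose levels below are assumptions, with FPI in µU/mL, the scale on which the constants 20 and 22.5 give plausible values. Write FPI = E + X, where E is the patient's own insulin and X is the injected insulin that the assay detects.

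**1. Absolute level.** Take FPG = 8 mmol/L and E = 5.

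| X | FPI | HOMA-β = 20 × FPI / 4.5 | HOMA-IR = 8 × FPI / 22.5 | Ratio to X = 0 |
|---|---|---|---|---|
| 0 | 5 | 22.2 | 1.78 | 1 |
| 5 | 10 | 44.4 | 3.56 | 2 |
| 10 | 15 | 66.7 | 5.33 | 3 |
| 15 | 20 | 88.9 | 7.11 | 4 |

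The ratio is (E + X) / E and does not depend on FPG. With E = 10 and X = 5 to 15 it is 1.5 to 2.5. If the assay detects none of the injected insulin, X = 0 and the ratio is 1.

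**2. Direct effect of a dose change.** Let s = X / (E + X) be the injected share of measured insulin, and let X move in proportion to dose. A 10% dose change with E and FPG fixed moves both indices by 10% × s. For s from 25% to 80% that is 2.5% to 8%.

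Larger sustained changes are handled elsewhere. SAP Section 6.6.1 counts an insulin change of more than 10% for at least 7 days as rescue, and Section 6.6.2 sets later values to missing in the observed-case (OC) analysis of efficacy endpoints. Table 6.7:1 places these biomarkers under efficacy, so the rule appears to cover them. The section that would confirm this is not in the public text.

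**3. Effect of falling glucose with a constant injected component.** Let FPG fall from 10 to 8 mmol/L with true secretory function unchanged.

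- HOMA-β on own insulin at FPG 10, with E = 5: 20 × 5 / 6.5 = 15.4.
- Own insulin giving the same value at FPG 8: E = 5 × 4.5 / 6.5 = 3.46.
- HOMA-β on measured insulin, with X unchanged:

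| X | At FPG 10: 20 × (5 + X) / 6.5 | At FPG 8: 20 × (3.46 + X) / 4.5 | Apparent rise |
|---|---|---|---|
| 5 | 30.8 | 37.6 | 22% |
| 10 | 46.2 | 59.8 | 30% |
| 15 | 61.5 | 82.1 | 33% |

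In general the apparent rise is s × (6.5 / 4.5 − 1) = 44% × s, with s taken at the first visit. No dose change is needed, so the OC censoring rule does not remove it. It becomes a difference between arms to the extent that FPG falls further on empagliflozin than on placebo. Protocol Section 1.2 describes the drug as lowering glucose independently of insulin.

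**4. Unit.** Section 5.4.1 prints FPI in mU/mL. Read literally, 10 µU/mL is 0.01 mU/mL. At FPG 8 this gives HOMA-IR 8 × 0.01 / 22.5 = 0.004 and HOMA-β 20 × 0.01 / 4.5 = 0.04, which would display as 0.0 and 0 under SAP Section 7. That display precision makes sense only for µU/mL (= mU/L).

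**The case against.** The strongest reply is that the plan already gives the beta-cell question to C-peptide: Section 5.4.1 says so, and SAP Table 6.7:1 gives C-peptide its own efficacy row. This stands. A reader might infer that the trial cannot address beta-cell function, and the documents do not support that. What remains wrong is that a second index, labelled as secretion, is built from a contaminated input.

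A reader might also infer that any dose difference between arms will show up as a false treatment effect. If the OC rule applies, sustained changes above 10% are censored, and the remaining direct effect is single-digit percent. That part of the reply stands. It does not reach the distorted baseline and absolute levels, or the glucose-driven rise in step 3.

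Nor do the indices measure the injected dose alone. They reflect own insulin plus detected injected insulin. Evening basal dosing is only suggested, the morning premixed dose is held, and assay detection is unknown, so contamination will vary between patients. Human insulins are also allowed, however, so the problem does not rest only on whether the assay detects analogues.

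Finally, some sections on further endpoints are not public, and a caveat there cannot be ruled out. The derivation in Section 5.4.1 is nevertheless current text, and SAP Section 6.6.6 refers back to it.

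**Conclusion.** The point holds, at low severity. As defined, HOMA-β cannot be read as endogenous insulin secretion in this population, and HOMA-IR is distorted in the same proportion. The size depends on assay detection, which the documents do not give.

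The 2- to 4-fold figure concerns absolute levels on assumed values and should not be quoted as bias in a randomised comparison, because all arms carry injected insulin at both visits. The relevant between-arm figures, also on assumed values, are about 2.5% to 8% for a 10% dose change and about 22% to 33% in HOMA-β for an FPG fall from 10 to 8 mmol/L. The second enters the comparison only through the difference in FPG change between arms.

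The printed unit may be no more than a lost micro sign. It does not show that the indices would be computed 1000-fold too small.

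Protocol Section 5.4 calls these biomarkers exploratory. The primary endpoint, the listed secondary endpoints, the hierarchical test and the sample size are unaffected.

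**What to change.** - In Protocol Section 5.4.1 and the matching SAP text, base the secretion index on fasting C-peptide and FPG at Visits 3 and 8, for example the fasting C-peptide to glucose ratio. Injected insulin does not add to C-peptide. State the formula in full, because the constants 20 and 22.5 belong to insulin and cannot be reused.
- Drop the FPI-based HOMA-β and HOMA-IR, or label them not interpretable under injected insulin wherever they appear, including the baseline table in SAP Section 7.1.
- Do not present fasting C-peptide alone as a replacement for HOMA-IR, since it is not a resistance index. If no suitable index is specified, say that insulin resistance is not assessed.
- If FPI is kept, state whether the assay detects the permitted insulins, and confirm the unit as µU/mL (= mU/L).

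The cost is a text and programming change. No new sample is needed: fasting insulin, C-peptide and FPG are already drawn together at both visits for the meal tolerance test (Protocol Section 5.1).

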#### 5.4.2 Pharmacogenomics biomarkers

Not applicable.

#### 5.4.3 Methods of sample collection

Additional biomarkers such as C-peptide and insulin will be determined according to the [Flow Chart](#). Further details about sample handling and shipment can be found in the ISF (Lab manual).

### 5.5 BIOBANKING

Not applicable.

## **5.6 OTHER ASSESSMENTS**

Not applicable.

## **5.7 APPROPRIATENESS OF MEASUREMENTS**

All measurements performed during this trial are standard measurements and will be performed in order to monitor safety aspects in an appropriate way.

The scheduled measurements are appropriate to see drug induced changes in vital signs, standard laboratory values, biomarkers specific to efficacy of treatment of T2DM, and ECG. The primary and secondary endpoints are standard and accepted for evaluation of safety and tolerability of an oral antidiabetic drug, and they are widely used in respective pivotal phase III studies.

Measurements of insulin and c-peptide will be conducted in order to characterise endogenous insulin production and will contribute to a better understanding of the influence of empagliflozin combination with insulin with or without OADs on the pathogenesis and possible recovery of diabetes in the patients.

Therefore, the appropriateness of all measurements applied in this trial is given.

## 6. INVESTIGATIONAL PLAN

### 6.1 VISIT SCHEDULE

All trial visits should take place in the morning. If a patient mistakenly takes trial medication in the morning of a visit before attending the clinic (excluding visits starting before randomisation) or comes in fed condition where a fasting condition is required (all visits), the visit should be rescheduled for another day (except screening) as soon as possible reminding the patient of the expected conditions. The rescheduled visit must take place in a short enough time-frame so that the patient has sufficient trial medication available.

All patients are to adhere to the visit schedule as specified in the [Flow Chart](#). If any visit has to be rescheduled, subsequent visits should follow the original visit date schedule. The trial medication packs contain sufficient medication to allow for these time windows. The run-in period must be 14-21 days long prior to randomization.

In the event of force majeure or other disruptive circumstances (e.g. pandemic) the investigational plan as per this clinical trial protocol may not be feasible at a site. With the consent of the patient, sponsor and investigator may agree on alternative, back-up or rescue methodology which may include but will not be limited to virtual patient visits and assessments, and direct-to-patient shipments of trial treatment.

If it is not recommended to conduct Visit 4, 5, 6 or 7 at the trial site, it may be performed remotely (via telephone and/or internet- based means of communication). In the event of a remote Visit 4, 5, 6 or 7 trial medication may be shipped by courier from site to patient, if legally acceptable according to local regulations and considered safe for patient to continue treatment. It is important that any remote Visit 4, 5, 6 and 7 is discussed with and approved by the sponsor/CRO to ensure delivery of trial medication fulfil the trial specific and country-specific requirements. All efforts should be made to at least perform two of the four visits with the patient visiting the site. The maximum time interval without a face to face contact with the patient should not exceed 16 weeks (e.g. the 12 week site visit could only be done remote if a face to face contact was performed at the 4 week or 8 week visit). The patient must be made aware of any conduct modifications and agreement needs to be obtained prior to them being implemented. See [Appendix 10.2](#) on the details of potential modification of trial conduct in case of restrictions due to COVID-19.

